5.6.2 Adverse Events

5.6.2.1 Definitions and Derivations

The MedDRA (version 24.1 at a minimum) will be used to code AEs. AEs will be graded according to the National Cancer institute Common Terminology Criteria for AEs (CTCAE) (using the CTCAE version 5.0).

AEs are defined as treatment emergent adverse events (TEAEs) if they onset or worsen (by investigator report of a change in intensity/severity), during the treatment emergent phase defined below. Worsening is determined by comparison with the pre-intervention severity of the AE recorded closest to the start of dosing.

When assigning AEs to the relevant phase of the study the following rules apply and any deviations must be agreed by the study team:

- Pre-treatment phase – All AEs with a start date after signing the informed consent form, prior to the first administration of IP that do not subsequently go on to worsen during the treatment emergent phase.
- Treatment emergent phase – All AEs starting or worsening in severity following the first administration of IP for the duration of the treatment period, up to and including 30 days after the last dose of IP as per the study safety follow-up period but prior to subsequent

cancer therapy. AEs with missing start time which occur on the same day as first IP administration will be reported as treatment emergent.

- Post-treatment phase – All AEs starting more than 30 days after last dose of IP or once subsequent cancer therapy is started, whichever is earlier. This period is defined for the purpose of possible causally related SAEs.

Serious Adverse Events (SAEs)

A serious adverse event (SAE) is any AE that:

- Results in death
- Is immediately life-threatening
- Requires inpatient hospitalization or prolongation of existing hospitalisation
- Results in persistent or significant disability/incapacity
- Is a congenital anomaly/birth defect in offspring of the participant
- Is an important medical event that may jeopardize the participant

AEs of special interest

An adverse event of special interest (AESI) is one of scientific and medical interest specific to understanding of the IP and may require close monitoring and rapid communication by the investigator to the sponsor.

The following events will be considered to be AESIs:

- Neutropenia, including Febrile neutropenia, Neutropenic sepsis, neutrophil count decrease
- Thrombocytopenia, including platelet count decrease
- Hepatotoxicity, including potential Hy's Law, Drug-induced liver injury, Bilirubin increase with transaminase (alanine aminotransferase [ALT] or aspartate aminotransferase [AST], or both ALT and AST) increase
- Pyrexia
- TLS
- Myocardial ischaemia

Other categories may be added, or existing terms may be modified as necessary. An AstraZeneca medically qualified expert after consultation with the Global Patient Safety Physician has reviewed the AEs of interest and identified which higher-level terms and which preferred terms contribute to each AESI. Further reviews may take place prior to database

lock to ensure any further terms not already included are captured within the categories. Preferred terms used to identify AESIs will be listed prior to database lock.

Other significant adverse events (OAE)

No OAEs are defined for this study.

5.6.2.2 Presentation

All TEAEs will be summarised and listed. AEs which are not treatment emergent will be listed for the Safety set.

TEAEs will be counted once for each participant for calculating percentages of participants experiencing TEAEs. In addition, if the same TEAE occurs multiple times within a particular participant, the highest severity and level of relationship observed will be reported. For tables by MedDRA SOC and MedDRA PT, participants with multiple TEAEs will be counted once for each SOC/PT.

An overall summary table of the number of participants experiencing each category of AEs will be produced. The number of participants experiencing TEAEs by MedDRA SOC and PT will be summarised and the severity, and relationship to IP will be summarised. Further splits by CTCAE grade, causal relationship to IP and AEs with Grade 3-4 will also be summarised.

Separate tables present AEs leading to discontinuation of IP, IP-related AEs, IP-related AEs leading to discontinuation of IP, AEs leading to dose reduction, AEs leading to dose delay, and AEs leading to dose interruption.

AEs leading to death will also summarised.

SAEs

SAEs will be summarised as described above for the TEAEs.

AEs of special interest

Grouped summary tables of certain MedDRA PTs will be produced and may also show the individual PTs which constitute each AESI grouping. Groupings will be based on PTs provided by the medical team prior to database lock, and a listing of the PTs in each grouping will be provided.

Summaries of the above-mentioned grouped AE categories include number and percentage (%) of participants who have:

- At least one AESI presented by event outcome

- At least one AESI causally related to IP
- At least one AESI leading to discontinuation of study intervention.

A summary of total duration (days) of AESI will be provided for events which have an end date, and this may be supported by summaries of ongoing AESIs at death and, separately, at data cut-off.

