Statistical Methods: In Module 1, the data cut-off (DCO) for the primary analysis for each cohort will occur after all response-evaluable participants in the cohort have had the opportunity to be followed for at least 6 months since their first dose or have progressed or have initiated other anticancer therapy, or when 75% of participants have progressed or died, whichever occurs first. Additional data cuts may also be performed, if required. At the end of each module a final analysis will be conducted to incorporate all data (up to and beyond the primary analysis) from all participants in the module. For all modules, the primary efficacy endpoint is ORR. For Module 1, ORR is measured in terms of the Lugano criteria. Secondary efficacy endpoints for Module 1 include CR rate, DoR, PFS and OS. Safety and tolerability will be assessed in terms of AEs, laboratory data, vital signs and ECG data for all modules. AEs will be graded according to the NCI CTCAE Version 5.0. The number and percentage of participants with TEAEs in different categories (eg, causally related, CTCAE Grade ≥ 3 , etc.) will be summarised by cohort; events in each category will be further summarised by MedDRA system organ class and preferred term. SAEs will be summarised separately if a sufficient number occurs. Data will be presented by cohort. Descriptive statistics will be used for all variables. Continuous variables will be summarised by the number of observations, mean, standard deviation, median, minimum, and maximum. Categorical variables will be summarised by frequency counts and percentages for each category. Unless otherwise stated, percentages will be calculated based on the population total by cohort and by timepoint as appropriate.

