9.4.3 Safety Analyses

Safety and tolerability will be assessed in terms of AEs, laboratory data, vital signs, and ECG changes. These variables will be collected for all participants. All safety data listings and summaries will be created using the safety analysis set.

Adverse events will be listed individually by cohort and participant. The number of participants experiencing each AE will be summarised by the MedDRA system organ class, MedDRA preferred term, and CTCAE grade (in line with NCI CTCAE Version 5.0). TLS will be graded by CTCAE grade and Howard's modification of Cairo-Bishop grading ([Appendix G; Howard et al 2011](#)). The number and percentage of participants experiencing each AE, and the number and percentage of participants with AEs in different categories (eg, causally related and CTCAE Grade ≥ 3) will be summarised by cohort, and events in each category will be further summarised by MedDRA system organ class and preferred term. SAEs will be summarised separately if a sufficient number occur.

Adverse event summary tables will include only treatment-emergent AEs. Adverse events will be defined as treatment-emergent if they have an onset or worsen (by investigator report of a change in intensity/severity), during the study treatment until the follow-up period (as defined in the individual study Modules), but prior to subsequent cancer therapy. AEs occurring outside of this period will be listed but not summarised.

During the evaluation of the AE data, an AstraZeneca medically qualified expert will review the list of AEs that were not reported as SAEs and AEs leading to discontinuation of study treatment. Based on the expert's judgement, AEs of particular clinical importance may, after consultation with the Global Safety Physician, be considered OAEs and reported as such in the CSR. A similar review of laboratory values, vital signs, ECGs, and other safety assessments will be performed for identification of OAEs.

Examples of these could be marked haematological and other laboratory abnormalities, and certain events that lead to intervention (other than those already classified as serious), dose reduction, or significant additional treatment. Duration of exposure will be summarised.

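### SAP 5.6.2.2 summarises Grade 3-4 AEs where the protocol names Grade ≥ 3; read literally, fatal events are missing from their own rows, and SAP Section 3 does not declare the change

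*SAP*

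**What the plan says.** Protocol 9.4.3 describes the core safety tables: "AEs in different categories (eg, causally related and CTCAE Grade ≥ 3) will be summarised by cohort", with a further breakdown by MedDRA term. The synopsis (protocol 1.1) has the same category: "participants with TEAEs in different categories (eg, causally related, CTCAE Grade ≥ 3 , etc.) will be summarised by cohort".

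SAP 5.6.2.2 plans a different one: "Further splits by CTCAE grade, causal relationship to IP and AEs with Grade 3-4 will also be summarised". It also sets a counting rule: "if the same TEAE occurs multiple times within a particular participant, the highest severity and level of relationship observed will be reported". SAEs are to be summarised in the same way as TEAEs.

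The same SAP section plans a separate summary of fatal AEs ("AEs leading to death will also summarised"), and SAP 5.6.3 adds a summary of deaths by category with a listing. SAP Section 3 declares three departures from the protocol: the Cycle 1 definition, the safety set and the survival sweep. The AE grade category is not among them.

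**The concern.** A severe-AE summary that stops at Grade 4 leaves out the worst grade. For a single preferred term, the highest-severity rule makes this perverse: a term recorded at Grade 4 and again at Grade 5 in one participant is reported at Grade 5, so it leaves its Grade 3-4 row because the outcome was worse.

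The events at issue are informative ones. Under protocol 8.3.8 and 8.3.12, events unequivocally due to progression are not AEs, and deaths clearly due to progression are not SAEs. Fatal AEs in these tables are therefore mainly deaths not clearly caused by the lymphoma. Protocol 10.9.2 says that safety and tolerability count toward the criteria for success, and with about 21 participants per cohort one or two cases would be visible.

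**Working it through.** The documents give no figure on this point, so there is nothing to reproduce. The check compares the texts and then illustrates the possible size.

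**1. Category.** Grade ≥ 3 covers Grades 3, 4 and 5. Grade 3-4 read literally omits Grade 5. I take CTCAE Grade 5 to mean a fatal AE; the documents spell this out only for the tumour lysis scale in protocol Appendix G.

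**2. Who is affected.** The highest-severity rule applies to repeats of the same TEAE in one participant. It does not assign each participant one worst grade across all AEs. So:

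- A Grade 5 event is absent from its own row in the Grade 3-4 summary.
- A participant whose only Grade ≥ 3 AE was fatal is absent from the any-event Grade 3-4 count.
- A participant with a fatal AE and a Grade 3-4 AE under another term stays in that count.

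**3. Weight of one participant.** If f participants had a fatal AE as their only Grade ≥ 3 event, the any-event count falls short by 100 × f/N percentage points. N = 21 is the planned response-evaluable number per cohort (SAP 4.2.3.7), 63 = 3 × 21, and 90 is the approximate maximum in protocol 1.1 and 10.9.2.

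| f (assumed) | N = 21 | N = 63 | N = 90 |
|---|---|---|---|
| 1 | 4.8 | 1.6 | 1.1 |
| 2 | 9.5 | 3.2 | 2.2 |
| 3 | 14.3 | 4.8 | 3.3 |

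**4. Range from overlap.** Assume 10 of 21 participants had any Grade ≥ 3 AE (47.6%), f of them with a fatal AE. The any-event Grade 3-4 row would then show:

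| f | None had another Grade 3-4 AE | All had another Grade 3-4 AE |
|---|---|---|
| 1 | 9/21 = 42.9% | 10/21 = 47.6% |
| 2 | 8/21 = 38.1% | 10/21 = 47.6% |
| 3 | 7/21 = 33.3% | 10/21 = 47.6% |

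**5. Can the other tables restore the Grade ≥ 3 count?** Not reliably. Adding the fatal-AE count to the Grade 3-4 count for f = 2 gives 8 + 2 = 10, which is correct, if there is no overlap. It gives 10 + 2 = 12, which is too high, if both participants are in both tables. The grade splits would give the count only if each participant were classified by maximum grade overall, which the SAP does not state.

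**The case against.** The case for leaving this alone has several sound parts.

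- The protocol introduces Grade ≥ 3 as an example, not as a defined endpoint; the Module 1 safety endpoint is simply CTCAE grade. This stands: the protocol names the category but does not fix it as a requirement.
- Fatal AEs are not lost. The grade splits, the fatal-AE summary, the SAE tables and the deaths summary all carry them. This stands, though none of these is stated to give the number of participants with any Grade ≥ 3 event.
- No decision rule uses this rate. The pausing rules in protocol 7.1.1 rest on specific events, including related deaths, and on the share of participants discontinuing for related AEs; the success criteria set no grade threshold. This also stands.
- The AESI summaries in SAP 5.6.2.2 are by outcome, causality and discontinuation, so they contain no grade split to correct. This stands.

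A reader might infer that every participant whose worst event was fatal drops out of the severe-AE table, so that the reported rate necessarily falls as toxicity becomes fatal. The documents do not support that. It would need a table classifying each participant by one worst grade, which the SAP does not specify. Overlap is also plausible: protocol 10.6.2.5 reports Grade 3/4 neutropenia at roughly 45% to 50% in earlier experience, so a participant with a fatal AE may well have had a separate Grade 3-4 event.

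**Conclusion.** The mismatch is real and undeclared. Followed literally, the SAP omits fatal events from their own rows in the Grade 3-4 summary and can understate the Grade ≥ 3 rate that the protocol named. The understatement of the any-event rate ranges from nil, with complete overlap, to 4.8 points per Grade-5-only participant in a cohort of 21.

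These sizes rest on an assumed number of fatal cases and on the planned response-evaluable numbers. Safety tables use everyone who received any amount of drug, so the denominator may be larger and the weight of one case smaller. The consequence is confined to the presentation and consistency of the safety tables. It does not conceal deaths, trigger or suppress any stopping rule, or affect the primary ORR analysis. It is still worth correcting because the correction is almost free.

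**What to change.** In SAP 5.6.2.2, replace the Grade 3-4 category with AEs of CTCAE Grade ≥ 3 and keep Grade 5 as its own line. Apply this to the TEAE tables, to the SAE tables that follow the same layout, and to IP-related AEs where they are split by grade. Add one sentence saying that a participant is counted if they had any Grade ≥ 3 event. No new AESI table by grade is needed.

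The cost is one phrase, one counting sentence and a table filter. The only downside is that the reported severe-AE rate may be slightly higher.

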8.3.1 Time Period and Frequency for Collecting AE and SAE Information

Adverse events and SAEs will be collected from time of signature of the ICF, throughout the treatment period and including the follow-up period of 30 days (\pm 7 days) after last dose of study intervention.

A formal assessment of AEs will occur at the visits marked in the SoA of the relevant module, but AEs reported at any time during the study must also be recorded in the eCRF.

If the investigator becomes aware of a SAE with a suspected causal relationship to the IMP(s) that occurs after the end of the clinical trial in a study participant, the investigator shall, without undue delay, report the SAE to the sponsor.

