8.3.2 Follow-up of AEs and SAEs

Any AEs that are unresolved at the participant's last assessment in the study are followed up by the investigator for as long as medically indicated, but without further recording in the eCRF. AstraZeneca retains the right to request additional information for any participant with ongoing AE(s)/SAE(s) at the end of the study, if judged necessary.

After the initial AE/SAE report, the Investigator is required to proactively follow each participant at subsequent visits/contacts. All SAEs and non-serious AEs will be followed until resolution, stabilisation, the event is otherwise explained, or the participant is lost to follow-up.

Adverse event variables

The following variables will be collected for each AE:

- AE (verbatim)
 - The capture of diagnoses is preferred over all associated signs and symptoms. For example: laboratory TLS, clinical TLS, cytokine release syndrome. Provisional diagnoses (eg, PHL) must be updated as soon as possible.
- The date when the AE started and stopped
 - When the onset of an AE in relation to dosing is rapid, for example TLS, it is important to record the **exact time of the start of infusion** dosing and the **time of AE onset** in addition to the dates.
- CTCAE grade/changes in CTCAE grade
- **For TLS events:** Adverse events of TLS shall be graded according to CTCAE. The AE verbatim shall discriminate between laboratory and clinical TLS. In addition, TLS events will be graded according to Howard modification of the Cairo-Bishop grading system (see [Appendix G](#)) on the TLS monitoring eCRF form.
- Whether the AE is serious or not

- Investigator causality rating against the IP(s) (yes or no)
- Action taken with IP(s) in response to the AE (for example: no action, dose reduced, treatment temporarily stopped, treatment permanently discontinued).
- Outcome of the event

In addition, the following variables will be collected for SAEs:

- Date AE met criteria for SAE
 - The date of start of first signs and symptoms should be captured together with the date the event became serious.
- Date investigator became aware of SAE
- Reason AE is classified as serious
- Date of hospitalisation
- Date of discharge
- Probable cause of death
- Date of death
- Autopsy performed (yes/no)
- Causality assessment in relation to Study procedure(s)
- Causality assessment to other medication

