4.1.3.6 Missing Dates

Generally, the imputation of dates is used to decide if an observation is treatment emergent for AEs or concomitant medications. The imputed dates should not be used to calculate durations, where the results would be less accurate.

The following are the guidelines used when partial dates are detected in the study:

- For missing diagnostic dates (eg, disease diagnosis), if the day and/or month are missing use 01 and/or January. If year is missing, put the complete date to missing.
- For missing AE and concomitant medication start dates, the following is applied:
 - Missing day – impute the 1st of the month unless month is the same as month of the first dose of the study drug then impute first dose date.
 - Missing day and month – impute 1st January unless year is the same as first dose date then impute first dose date.

- Completely missing – impute first dose date unless the end date suggests it could have started prior to this in which case impute the 1st of January of the same year as the end date.
- Imputed start date should be no later than the end date.
- For missing AE and concomitant medication end dates, the following is applied:
 - Missing day – impute the last day of the month unless both the month and year are the same as the last dose date or the primary analysis date cut-off (DCO) date then impute the last dose date or the primary analysis DCO date.
 - Missing day and month – Impute 31st December unless the year is the same as the last dose date or the primary analysis DCO date then impute the last date or the primary analysis DCO date.
 - Completely Missing – before imputing a date, consider whether the AE/medication is still ongoing and also when it started in relation to study drug. If the ongoing flag is missing then assume that AE is still present/ medication is still being taken (ie, do not impute a date). If the AE/medication has stopped and start date is prior to first dose date, then impute first dose date. Or if it started on or after first dose date then impute a date that is after the last dose of study drug date.
- Flags will be retained in the database indicating where any programmatic imputation has been applied, and in such cases for AEs and concomitant medications, any durations will not be calculated.

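### The AESI duration summary covers resolved events only, so it understates duration. The effect is small for short events and material for prolonged ones.

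*SAP*

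**What the plan says.** SAP 5.6.2.2, under AEs of special interest, makes one firm commitment on duration: "A summary of total duration (days) of AESI will be provided for events which have an end date". The sentence continues: "and this may be supported by summaries of ongoing AESIs at death and, separately, at data cut-off". The duration table is therefore certain and the ongoing-event summaries are discretionary. The same section also commits to counts of participants with "At least one AESI presented by event outcome", and says "All TEAEs will be summarised and listed".

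Three other provisions decide which events have a usable duration:

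- Protocol 8.3.1 collects AEs from consent "throughout the treatment period and including the follow-up period of 30 days" (± 7 days) after the last dose.
- Protocol 8.3.2 has AEs that are unresolved at the last assessment followed "for as long as medically indicated, but without further recording in the eCRF".
- SAP 4.1.3.6 treats an AE with a completely missing end date and no ongoing flag as still present. For AEs with imputed dates it adds: "in such cases for AEs and concomitant medications, any durations will not be calculated".

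SAP 4.1.3 names Kaplan-Meier for time-to-event variables where appropriate, and SAP 5.2.3 applies it with censoring to duration of response. Neither section assigns it to AESI duration.

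**The concern.** Whether an event has an end date depends on how long it lasts relative to the time left for recording. Restricting the summary to events with an end date selects on the quantity being measured, and the selection favours shorter durations. The optional summaries would show how many events were ongoing. Nothing says that they would report durations or change the estimate.

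Duration is relevant here because the protocol's benefit-risk argument relies on reversibility. Sections 2.3.1 and 10.6.2.2 describe hepatic events as resolving quickly, and the dose-modification tables in 10.6.1 turn on recovery within set times. An unlabelled median from resolved events only leans towards confirming that picture.

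**Working it through.** The plan states no figure for AESI duration or for the share ongoing, so there is nothing to reproduce. The calculations below are illustrative.

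**Model A: recording continues to 30 days after the last dose (Protocol 8.3.1).** Assumptions not in the documents:

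- event duration is exponential with median m days;
- treatment length is exponential with median M = 56 or 112 days (8 or 16 weeks);
- onset is uniform over treatment.

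With r = M/m, the share of events still ongoing when recording stops is

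p = 2^(−30/m) × ln(1 + r)/r.

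Every event has at least 30 days of recording in this model. While the answer is below 30 days, the median among events with an end date solves 1 − 2^(−x/m) = (1 − p)/2, which gives

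x = m × [1 − log2(1 + p)].

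Worked case, m = 28 and M = 56: r = 2; p = 0.476 × 0.549 = 0.261; x = 28 × (1 − 0.335) = 18.6 days.

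| True median (days) | Ongoing, M = 56 | Reported median, M = 56 | Ongoing, M = 112 | Reported median, M = 112 |
|---|---|---|---|---|
| 4 | 0.1% | 4.0 | 0.1% | 4.0 |
| 7 | 1.4% | 6.9 | 0.9% | 6.9 |
| 14 | 9.1% | 12.2 | 6.2% | 12.8 |
| 28 | 26.1% | 18.6 | 19.1% | 20.9 |

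For a true median of 28 days the true mean is 28/ln 2 = 40 days. Simulation with M = 56 puts the mean of resolved events at about 24 days. A Kaplan-Meier median that censored ongoing events came within 0.1 day of the true value in every row.

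**Model B: recording can stop at any time after onset**, as it can at data cut-off, death or withdrawal. Duration is again exponential. Time from onset to the end of recording is assumed uniform on 0 to F days. One million events were simulated per scenario.

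| True median (days) | Reported median, F = 60 / 120 / 180 | Ongoing, F = 60 / 120 / 180 |
|---|---|---|
| 4 | 3.6 / 3.8 / 3.9 | 9.7% / 4.8% / 3.2% |
| 7 | 5.8 / 6.4 / 6.6 | 16.8% / 8.4% / 5.6% |
| 14 | 9.2 / 11.6 / 12.4 | 32.0% / 16.8% / 11.2% |
| 30 | 12.7 / 19.1 / 22.5 | 54.1% / 33.8% / 23.6% |
| 60 | 14.9 / 25.5 / 32.9 | 72.1% / 54.1% / 42.1% |

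Kaplan-Meier was within about 1 day of the truth throughout. Across these scenarios, 3% to 15% of the excluded events had a true duration below the reported median, so exclusion does not pick out only long events.

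Model A is closer to the protocol for participants who complete the 30-day follow-up. Model B shows how the gap grows when recording is cut short. Both treat censoring as independent of duration.

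**The case against.** The strongest reply is that the bias will be negligible for most AESIs in this trial. Protocol 10.4.2 describes earlier Grade 4 AST elevations as lasting less than 4 days. Sections 2.3.1 and 10.6.2.2 say that liver events resolved rapidly, and 10.6.2.5 says that neutropenia usually recovers spontaneously. Under 10.6.2.1.2, participants with TLS stay in hospital until it resolves. Nothing suggests a typical duration near 28 days. This stands, and it puts most events in the upper rows of the tables. It does not cover thrombocytopenia, whose duration is not stated, or the minority of events that fail to resolve.

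Second, unresolved events are not hidden. The outcome table and the TEAE listings are firm commitments, and SAP 5.6.4.2 commits to laboratory box plots by timepoint and to liver-test plots over time. Protocol 8.3.2 also asks for follow-up to resolution or stabilisation and lets the sponsor request more information. Appendix E 4.2 has potential Hy's Law cases monitored until return to normal or baseline, with follow-up SAE forms. A reader might infer that unresolved events can never acquire an end date, or that the plan ignores them. The documents do not support either reading. These provisions disclose unresolved events, however, and leave the duration statistic as it is.

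Third, time to resolution is not among the listed AE endpoints, the table is descriptive, and it states its own restriction. That lowers the stakes but does not remove the bias.

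**Conclusion.** The point holds in a limited form. The rule excludes unresolved events and pulls the reported duration downward, and the plan contains no firm correction. Events with imputed dates also drop out, with no clear direction of bias.

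Under Model A the understatement is at most about 0.1 day for true medians of 4 to 7 days, 1 to 2 days for 14, and 7 to 9 days for 28. Model B gives larger gaps where recording is cut short. All of this depends on assumed exponential durations and assumed recording times.

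A reader might infer that the longest events are systematically dropped, or that AESIs in general will look more reversible than they are. The documents support neither. What is dropped is the unresolved events, some of them short with late onset, and the protocol's own descriptions point to mostly short hepatic and neutropenic events. The practical exposure is prolonged cytopenias and non-resolving liver events. ORR and the other efficacy analyses are unaffected.

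**What to change.** In SAP 5.6.2.2:

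1. Label the existing table *resolved events only*.
2. Change *may* to *will* for the summaries of AESIs ongoing at death and at DCO.
3. Report the number of events excluded from the duration table, by reason (ongoing, imputed date).
4. Where event numbers allow, add a Kaplan-Meier time to resolution. Use the first event per participant per AESI category, and censor ongoing events at the earliest of last AE assessment, death or DCO. The first event is preferable to the longest, because choosing the longest would bias durations upward.
5. Add a caveat that censoring at death, or at discontinuation caused by the event, may be informative.

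Items 1 to 3 are wording changes and counts. Item 4 is one more output from a method the SAP already uses for duration of response. With about 21 participants per cohort, some categories will have too few events for a useful curve, and items 1 to 3 are then sufficient.
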